Use of these "third generation" ECIGs is rising (e.g., Barrington-Trimis et al., 2017) and, relative to lower power devices, they can produce more carcinogens (Gillman et al., 2016; El-Hellani et al., 2016) and lead users to consume more liquid (e.g., Wagener et al., 2017; Etter, 2016a). These results suggest that, when higher power devices are available, the intended consequences of the EU directive are less likely to be realized and unintended consequences (more liquid consumed) are more likely to occur. The ability to predict the effects of regulatory action might help FDA craft policies that are more likely to meet their intent while limiting unintended consequences. Indeed, if FDA had scientific methods that could predict these population-level outcomes, these methods could be used to generate data to guide the development of potential regulation. Our goal with this study is to provide these methods to FDA. To do so, we use behavioral economic indices of abuse liability to examine the effects of limiting device power and nicotine concentration.

2. * Describe the study hypothesis and/or research questions. Use lay language whenever possible.

The purpose of this study is to determine if abuse liability indices will be impacted by differences in electronic cigarette (ECIG) nicotine concentration and device settings (voltage and resistance settings, which determine's the devices power level) among groups of Dual Users (tobacco cigarette and ECIG users) and ECIG exclusive users.

We hypothesize that as nicotine concentration is lowered, abuse liability indices will be lowered, as assessed by less willingness to pay/work for ECIG puffs and more price sensitivity, but that these effects will be offset by higher power. Also, relative to dual ECIG+TCig users, exclusive ECIG users will exhibit larger reductions in abuse liability at lower nicotine concentrations. This pattern highlights how limiting liquid nicotine alone may not alter overall ECIG abuse liability in markets where higher power devices allow nicotine intake to be maintained.

3. * Describe the study's specific aims or goals. Use lay language whenever possible.

The aims of this study are to better understand how power settings of electronic cigarettes (ECIGs) combined with liquids of differing nicotine concentrations impact several measures of abuse liability.

Results will be used to inform future tobacco product regulations of these device features/characteristics.

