4. * Describe the scientific benefit or importance of the knowledge to be gained:

The benefits of this research are of a scientific nature. Specifically, we aim to use study results to inform our understanding of the abuse liability of ECIG device features/characteristics as well as provide information to guide appropriate regulation of ECIGs. We anticipate long term benefits to the public at large by adding to the limited body of knowledge involving these devices among ECIG only users and dual cigarette and ECIG users.

5. * Describe any potential for direct benefits to participants in this study:

None.

6. Upload a supporting citation list if applicable:

ID: HM20012696

View: SF2 - Study Population

Study Population

1. * Provide the maximum number of individuals that

1. May participate in any study interaction or intervention (Including screening, consenting, and study activities)

AND/OR

2. You obtain any data/specimens about (regardless of identifiability)

at VCU and at other sites under the VCU IRB's oversight. See the help text for additional guidance.
300

2. If this is a multi-Center Project, what is the maximum anticipated number of subjects across all sites?

3. * Provide justification for the sample size by explaining how you arrived at the expected number of participants and why this number is adequate for answering the research questions:

120 completers (60 ECIG exclusive users and 60 Dual ECIG and Tobacco Cigarette users) are required to achieve greater than 80% given $p < 0.05$ for the breakpointMCP and breakpointPRT. We excluded own brand controls to ensure we are powered to detect differences across experimental conditions.

We estimate up to 300 individuals may be consented over the course of the study. Please note that initial telephone/web screening is performed under separate protocols - HM20007677 and HM20002567.

4. * List the study inclusion criteria:

General Inclusion:

Age 21 – 55 (verified by photo ID), willing to provide informed consent, they must agree to attend the lab and abstain from tobacco/nicotine as required and able to provide a semi-quantitative urine cotinine result of 'positive' at screening.

ECIG exclusive Inclusion:

Reports using ≥ 1 ml of ECIG liquid/day or approximately one pod/cartomizer per day of at least 3 mg/ml nicotine for the past 3 months or longer and no tobacco cigarette consumption within the past 30 days.

Dual ECIG and Tobacco Cigarette User Inclusion:

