Overview. This study involves 60 current E-Cigarette (ECIG) only users and 60 Dual Users (ECIG + traditional tobacco cigarette) who will complete 5, within-subject, laboratory conditions that differ by the product used: 1) ECIG with low mg/ml; low watts, 2) ECIG with low mg/ml; high watts, 3) ECIG with high mg/ml; low watts, 4) ECIG with high mg/ml; high watts, and 5) own brand (ECIG or tobacco cigarette). The first ECIG 4 conditions will be Latin-square ordered and single blinded such that the participants will not know which condition is administered in each ECIG session. The last condition for all subjects will be their own brand. For ECIG users it will be their own brand ECIG. For Dual Users it will be either own brand ECIG or tobacco cigarette. To allow for comparisons between groups (ECIG vs Dual) for this own brand condition, we will aim for a majority of the Dual User sample to receive their own brand ECIG in the last session.

Participants. A total of 120 adults (ages 21-55) who currently use ECIGs only or dual ECIG and tobacco cigarettes will be enrolled. We will attempt to recruit an equal number of men and women of diverse racial/ethnic backgrounds, although this study is not intended to address gender or race/ethnic differences.

Inclusion criteria: To be included, participants must be healthy, as determined by self-report and heart rate/blood pressure (HR/BP) check, between the ages of 21-55 (as verified by photo ID), and willing to provide informed consent. They must agree to attend the lab and abstain from tobacco/nicotine as required, to use the designated products, and to follow the study protocol.

Participants must also be either A) ECIG only users [reports using ≥ 1 ml of ECIG liquid/day or approximately 1 pod/cartomizer/day of at least 3 mg/ml nicotine for the past 3 months or longer and no tobacco cigarette consumption within the past month] or B) Dual ECIG + traditional tobacco cigarette smokers [reports daily use of ECIG (≥ 3 mg/ml nicotine) or tobacco cigarettes (any frequency) AND some day use (≥ 3 days per week) of ECIGs (≥ 3 mg/ml nicotine) or tobacco cigarettes (any frequency)] use for the past 3 months or longer] who can provide a semi-quantitative urine cotinine result of 'positive' at screening (urine cotinine cassette test).

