Importantly these tasks are programmed to end early if participants report zero consumption for assessed products. Estimated time per measure is <3 min, and each measure will only be completed once per session.

The Multiple Choice Procedure (MCP) questionnaire consists of three columns and 15 rows. Ten puffs from the session specific product (session specific ECIG or Own Brand ECIG/Cigarette) will be shown in the center column while varying amounts of money (\$0.01 - \$10.24) will be presented in ascending order in right column. Participants will be instructed to circle whether they prefer puffs or money for each of the 15 choices given to them. The MCP will only be administered once, immediately following the DPT. Immediately after the questionnaire is completed, participants will be presented with one of their choices (drawn randomly) and given a 10-minute 'consumption' period in which to take puffs or receive money. After the consumption period, participants will rest for 10 minutes before either ending the session or beginning the 60-minute rest period.

Subjective measures. Repeatedly within each condition we will use the Minnesota Nicotine Withdrawal Scale and the Direct Effects of Nicotine Scale to measure nicotine withdrawal symptoms before and after each behavioral measure.

Data analysis. Subjective, physiological, DPT, MCP, and PRT data will be prepared as reported elsewhere ([name] et al., 2017; Rusted et al., 1998; [name] et al., 2010). Elasticity is estimated using an exponential demand function with nonsystematic DTP data excluded based on two criteria: trend, or whether the participant had a general decrease in consumption from the lowest to highest price; and bounce, or whether a participant reported higher consumption at sequential higher prices (Stein et al., 2015). In general, analysis will involve a mixed (between- and within-subject) ANOVA. Demographic data will be examined to determine if there are significant between-group differences on measures that may be related to study outcomes (some differences are expected, like cigarette use). Unexpected between group differences will be considered as potential covariates in the primary analysis (see Evans et al., 2006). For all ANOVAs, adjustments for sphericity violations and post-hoc testing using Tukey's HSD or planned contrasts with Bonferroni corrections will be used (Keppel, 1991). Missing data will be imputed using multiple imputation techniques (Allison, 2001).

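### Planned contrasts use Bonferroni; Holm's step-down version gives the same 5% family-wise control and never rejects less, a cheap gain of 0 to about 12 points of power per real contrast

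*Protocol*

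**What the plan says.** The Data analysis paragraph of the protocol (Study Procedures, item 7) and the SAP carry the same text. The main analysis is described only in outline: "In general, analysis will involve a mixed (between- and within-subject) ANOVA". For follow-up comparisons the plan names two routes joined by 'or', "post-hoc testing using Tukey's HSD or planned contrasts", and for the second route "planned contrasts with Bonferroni corrections will be used". No step-down version is mentioned. The plan does not list or count the planned contrasts, define the family, or say when each route applies.

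The design has "5, within-subject, laboratory conditions that differ by the product used": four study-ECIG conditions (two nicotine concentrations by two wattages) and own brand. The sample-size justification (Study Population, item 3) asks for 120 people to finish the study, 60 in each user group, and says that these "are required to achieve greater than 80% given $p < 0.05$ for the breakpointMCP and breakpointPRT". On the scope of that statement it adds: "We excluded own brand controls to ensure we are powered to detect differences across experimental conditions". No effect size, SD, within-person correlation or number of comparisons is given.

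**The concern.** Plain Bonferroni tests every one of m contrasts at 0.05/m. Holm uses that threshold for the smallest p-value only and relaxes it for each later one, with the same error guarantee. For testing, the plain version therefore gains nothing over Holm.

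The difference matters when several effects are real together, and the hypotheses (Background, Rationale and Goals, item 2) expect more than one: nicotine, device power, and a nicotine effect that differs by user group. The power statement refers to p < 0.05 and mentions no multiplicity, so a contrast sized at that level loses power under any correction. At stake is whether the pattern across the four study-ECIG conditions is picked up in full or in part. The validity of the trial is not in question.

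**Working it through.** **1. The plan's own figure.** The stated N = 120 with more than 80% power can be neither reproduced nor refuted, because no effect size, SD or correlation is given. Back-solving at two-sided 0.05 (sidedness assumed) and 80% power, with 1.960 + 0.842 = 2.802:
- within-person effect, all participants: 2.802/√120 = 0.256 SD of the paired difference
- within one group of 60: 2.802/√60 = 0.362
- between groups of 60: 2.802 × √(2/60) = 0.51

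The documents do not say which was meant. Step 4 assumes a paired effect of 0.258 SD, which gives 80% uncorrected power with t-tests.

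**2. The two rules.** Bonferroni rejects contrast i if p_i ≤ 0.05/m. Holm orders the p-values and rejects the j-th smallest if it is ≤ 0.05/(m − j + 1), stopping at the first failure. For m = 4 the Holm thresholds are 0.0125, 0.0167, 0.025 and 0.05, against 0.0125 throughout. No Holm threshold is smaller, so Holm rejects at least what Bonferroni rejects.

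Error control: with m0 true nulls, the first one to be rejected has at most m − m0 rejections before it, so its threshold is at most 0.05/m0. The chance that any of the m0 null p-values is that small is at most m0 × 0.05/m0 = 0.05, with no assumption about dependence. If every null is true, both rules reject something under the same condition (smallest p ≤ 0.05/m).

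**3. Size for a general family.** Assumed: 80% unadjusted power per real contrast. Bonferroni power is Φ(2.802 − z), where z is the normal quantile at 1 − 0.025/m. For m = 6, z = 2.638 and Φ(0.164) = 56.5%. Holm's power is simulated (at least 200,000 replicates). Entries are Bonferroni v Holm for independent contrasts.

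| m | all real | half real | one real |
|---|---|---|---|
| 6 | 56.4% v 68.2% | 56.6% v 59.8% | 56.4% v 56.5% |
| 10 | 49.8% v 61.0% | 49.8% v 53.0% | 49.6% v 49.7% |

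Over the settings run (contrast correlation 0 and 0.5), the gain was 5.2 to 11.8 points with all contrasts real (m = 2 to 10), 2.2 to 3.2 with half real (m = 4 to 10), and 0.0 to 0.2 with one real. Varying the unadjusted power from 50% to 95% widens these to 2.3–14.5, 0.9–3.9 and 0.0–0.3. With some true effects present, Holm's simulated family-wise error was at most 0.048.

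**4. Size in this design.** A 2×2 within-person model of the four study-ECIG conditions, N = 120, equal correlations, paired effect 0.258 SD. Power per real single-factor contrast, Bonferroni v Holm (approximate):

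| True pattern (assumed) | six pairwise contrasts | four simple effects |
|---|---|---|
| Nicotine and power additive, equal | 56% v 65% | 61% v 72% |
| Nicotine only | 55–56% v 60–61% | 61% v 63% |
| Only low-nicotine/low-watt differs | 56% v 59% | 61% v 63.5% |

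In the additive case, power to detect every real contrast rises from about 12% to 28–29% (six contrasts) or from 18% to 42% (four). Power to detect at least one contrast hardly moves (at most about 0.3 point).

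**5. What the change does not touch.** If the mixed ANOVA is coded as the 2×2 (the coding is not stated), the nicotine main effect averages two paired differences. Its standardised effect in the same model is 0.258 × √2 = 0.365, and 0.365 × √120 = 4.0, so power is about 98% at 0.05 whichever follow-up correction is used. If it were instead one of three corrected contrasts (nicotine, power, interaction), power would be about 94% v 96%, a gain of about 1.5 points.

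**The case against.** The case for leaving the plan alone has several sound parts.

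- Bonferroni is valid and conservative, and it has matching simultaneous confidence intervals; Holm has no simple equivalent. This stands: the point concerns efficiency and is not an error in the plan.
- The protocol's own hypothesis is that lower nicotine reduces abuse liability, "but that these effects will be offset by higher power". That implies some small or null contrasts, and under one reading (only the low-nicotine/low-watt condition differs) the gain is 2 to 3 points. This stands too. A reader might infer that the plan gives up 5 to 12 points on every contrast. That range needs every contrast to be real with about 80% unadjusted power, which the documents do not say.
- All six pairwise comparisons are the usual use of Tukey's HSD, which the plan also allows. Where Tukey is used, the proposed change does nothing.
- A reader might infer that Bonferroni would produce a false finding of no nicotine difference, to be read as support for the claim that nicotine limits alone do not work. The documents do not support this. The ANOVA's own terms are unaffected (step 5). The claim is confined to markets where higher-power devices let users maintain nicotine intake. The first hypothesis predicts a nicotine effect, so missing one would count against it.

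What survives is narrow. On the planned-contrast route, Holm costs nothing in error control and can only add rejections.

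**Conclusion.** The point holds as an inexpensive improvement. That Holm keeps family-wise error at 5% and never rejects less than Bonferroni needs no input that the documents lack. The size of the benefit does need such inputs. At an assumed 80% unadjusted power it is 0 to about 12 points per truly non-null contrast: about 10 if nicotine and power effects are additive, about 2 to 5 if only nicotine matters or only the low-nicotine/low-watt condition differs, and near zero if one contrast is real. Because neither the contrasts nor their effects are stated, none of these figures can be called the loss in this trial. The benefit is confined to the planned-contrast route.

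**What to change.** In the Data analysis paragraph of the protocol and in the SAP, replace the phrase on Bonferroni-corrected planned contrasts with: planned contrasts with Holm (step-down Bonferroni) adjusted p-values at family-wise 5%. Leave the Tukey option as it is. Do not tie the phrase to a single error term, because a group-by-nicotine contrast compares two independent groups of 60 and needs a between-group test of the paired differences.

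The cost is one phrase in each document and a standard software option, with no extra participants, data or alpha. If simultaneous intervals are wanted, report Bonferroni intervals alongside and note that one may include zero for a contrast that Holm declares significant. Holm, like Bonferroni, can be applied only to a defined family, so the contrasts have to be listed before either is used.

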Reports daily use of ECIGS (≥ 3 mg/ml nicotine) or tobacco cigarettes (any frequency) AND someday use (≥ 3 days per week) of ECIGS (≥ 3 mg/ml nicotine) or tobacco cigarettes (any frequency) for the past 3 months or longer.

5. * List the study exclusion criteria:

Individuals with the following self-reported current, diagnosed medical condition(s) will be excluded automatically: heart-related conditions (e.g., recent heart attack/stroke, coronary heart disease), severe immune system disorders (e.g., HIV/AIDS, multiple sclerosis), respiratory disorders (e.g., COPD, asthma), kidney diseases, liver diseases (e.g., cirrhosis), or seizures,

Individuals with other self-reported current, diagnosed medical conditions (e.g., diabetes, thyroid disease, Lyme disease) will be considered for exclusion after consultation with the PI and medical monitor. Participants with any medical condition/medication that may affect participant safety, study outcomes, or biomarker data will be excluded based on these consultations.

Participants with self-reported current, diagnosed psychiatric conditions or who report current psychiatric treatment or psychotropic medication use will be excluded.

Individuals with past month use of cocaine, opioids, benzodiazepines, methamphetamine, or other illicit drugs. Self-report of >15 days out of the past 30 for marijuana use, or >25 days out of the past 30 for alcohol use.

Individuals who report using any other tobacco products on a weekly or more frequent basis will be excluded.

Women who are breast-feeding or test positive for pregnancy (by urinalysis at screening) will be excluded.

Individuals intending to quit tobacco/nicotine products in the next 30 days will also be excluded and referred to tobacco cessation treatment.

In addition, participants who have previously participated in a study with exactly the same manipulations of ECIG type, setting, and liquid nicotine concentration will be excluded. Individuals enrolled in HM20012738 will be excluded from the current study. Staff from this protocol will work with staff (who are also listed on this protocol) to assure that there is no cross participation between studies.

6. * Will individuals with limited English proficiency be included in or excluded from this research?

- Included
- Excluded - safety concerns if participants are unable to communicate with the study team
- Excluded - instruments/measures only validated in English**

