Exclusion criteria: Individuals with the following self-reported current, diagnosed medical condition(s) will be excluded automatically: heart-related conditions (e.g., recent heart attack/stroke, coronary heart disease), severe immune system disorders (e.g., HIV/AIDS, multiple sclerosis), respiratory disorders (e.g., COPD, asthma), kidney diseases, liver diseases (e.g., cirrhosis), or seizures, Individuals with other self-reported current, diagnosed medical conditions (e.g., diabetes, thyroid disease, Lyme disease) will be considered for exclusion after consultation with the PI and medical monitor. Participants with any medical condition/medication that may affect participant safety, study outcomes, or biomarker data will be excluded based on these consultations. Participants with self-reported current, diagnosed psychiatric conditions or who report current psychiatric treatment or psychotropic medication use will be excluded. Individuals with past month use of cocaine, opioids, benzodiazepines, methamphetamine, or other illicit drugs will be excluded as well as those who self-report of >15 days out of the past 30 for marijuana use, or >25 days out of the past 30 for alcohol use. Individuals who report using any other tobacco products on a weekly or more frequent basis will be excluded. Women who are breast-feeding or test positive for pregnancy (by urinalysis at screening) will be excluded. Those who intend to quit tobacco/nicotine products in the next 30 days will also be excluded and referred to tobacco cessation treatment. Individuals enrolled in HM20012738 will be excluded from the current study.

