Procedure. For each session, participants will be asked to refrain from tobacco/nicotine use for ≥ 12 hours and eating food/drinking caffeinated beverages for 1 hour prior to their scheduled session with verification of tobacco/nicotine use status upon arrival at the lab (expired air CO ≤ 7 for ECIG users and ≤ 10 ppm for Dual Users). At the start of the

session, participants rest for 30 minutes, at this time participants will be asked about symptoms experienced since last visit. During this time, participants will not be allowed to use their phones, eat or drink outside beverages but we will provide water to drink and they are invited to read books/magazines or watch movies that we provide to them. Thirty minutes (min) after session onset, participants will sample the session-specific product (2 puffs) followed by a 1 hour rest period, following the same guidelines as the first 30-minute rest period. After the rest period, baseline subjective measures to assess tobacco abstinence symptoms will be completed. Immediately after either the PRT or the DPT/MCP tasks will be completed. The PRT takes approximately 40 minutes to complete and the DPT/MCP takes approximately 40 minutes to complete. Please note that this order, PRT – DPT/MCP or DPT/MCP – PRT, is counterbalanced across participants to control for the effects of completing one task set prior to the other. Following the 1st counterbalanced task assessment, participants will complete a 60-minute rest period. The study procedures should take no more than 240 minutes or 4 hours but study procedures could be completed earlier than that based on decisions the participant makes during the PRT.

0m – CO Check; Physio data collection begins, additional questions about symptoms asked.

30m – 2 puff sample

90m – CO Check; Subjectives measure 1

100m – DPT/MCP OR PRT

140m – Behavioral Measure 1 completed

Subjectives measure 2

Begin 60m rest period

200m – Subjectives measure 3

DPT/MCP OR PRT

240m – Behavioral Measure 2 completed

Subjectives measure 4

end session

Product administration will consist of a 2 sample puff at the beginning of each session. Three behavioral choice tasks will be performed (DPT, MCP, and the PRT). Two of those, (The MCP and the PRT) may yield additional puffs, depending on the decisions made. See the Behavioral Measures section below for more details.

Measures.

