Other ECIG related side effects may include a sore or scratchy throat and headache. In addition, some people who use e-cigarettes have experienced seizures (<https://www.fda.gov/tobacco-products/ctp-newsroom/some-e-cigarette-users-are-having-seizures-most-reports-involving-youth-and-young-adults>). These have been reported among individuals with a history of seizures as well as among individuals using other substances such as marijuana and amphetamines, as well as among others. In addition, recently there have been many cases of e-cigarette use being associated with respiratory illnesses such as difficulties breathing, shortness of breath, cough and/or chest pain before hospitalization. In some cases, e-cigarette use has led to death and the Centers for Disease Control and prevention has advised people to stop vaping. In some cases symptoms of mild to moderate gastrointestinal illness such as nausea, abdominal pain, vomiting, diarrhea or fevers or fatigue have been reported.

Participants also might experience side effects from products that contain nicotine such as acute increases in heart rate and blood pressure, sweating, lightheadedness, dizziness, nausea, and nervousness. The ECIG liquid used may contain more nicotine than participants normally use.

These effects are unlikely in individuals who use e-cigarettes/cigarettes regularly.

There is some risk of illness/contamination due to ECIGs being reused between participants.

There is some risk of loss of confidentiality.

In addition, recently (as of September 2019) there have been many cases of e-cigarette use being associated with respiratory illnesses such as difficulties breathing, shortness of breath and/or chest pain before hospitalization. In some cases, e-cigarette use has led to death, and the Centers for Disease Control and Prevention has advised people to stop vaping. In some cases symptoms of mild to moderate gastrointestinal illness such as vomiting, diarrhea, or fevers or fatigue have been reported.

2. * Describe how each of the risks/harms/discomforts identified above will be minimized:

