Tobacco/nicotine abstinence syndrome: As individuals entering this study may exhibit signs of nicotine dependence there is a possibility that during the 12-hour tobacco/nicotine abstinence period prior to each session, participants may experience symptoms associated with tobacco/nicotine abstinence including irritability, anxiety, restlessness, hunger, and difficulty sleeping. Importantly these effects can be uncomfortable but are not medically dangerous. Participants will be informed of these potential abstinence-related side effects during the informed consent.

During the sessions, if the participant reports experiencing small droplets of ECIG liquid during inhalation, we will immediately replace the device he or she is using in the session.

We will inform participants of the other ECIG-related side effects during the informed consent process.

The risk of seizures is minimized by excluding participants with any history of seizures, and by having a full-time RN available, as well as monitoring of vital signs. In addition, some of the reported seizures occurred in users who were using other substances such as marijuana or amphetamines--the risk of seizures in this study is reduced as we are administering nicotine and no other substances.

The risk of respiratory illnesses related to ECIG use is minimized by the limited ECIG use that occurs in each session (10 puffs plus a 60 minute ad lib use period). Participants are informed about recent reports of ECIG-related respiratory

illnesses and are informed that the CDC has advised people to stop vaping. Participants are also advised to monitor themselves for symptoms and to seek medical attention if they have concerns. In addition, we will ask about respiratory and gastrointestinal symptoms at screening and before each session begins. Answers given at the beginning of each session will be compared to the participants' previous answers, and if any symptoms have increased, [name] will be asked to review the symptoms. In some cases, we may contact [name] to determine if a session can proceed.

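### The risk section relies on excluding anyone with any history of seizures, but the exclusion lists cover seizures only as a current, diagnosed condition

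*Protocol*

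**What the plan says.** On the Risks, Discomforts, Potential Harms and Monitoring page, question 1 lists seizures among the risks of e-cigarette use and says of the reported cases: "These have been reported among individuals with a history of seizures", as well as among others. Question 2 gives the protection: "The risk of seizures is minimized by excluding participants with any history of seizures". It adds that a nurse is available, that vital signs are monitored, and that the study gives nicotine and no other substance.

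Eligibility is set out twice, under Study Population question 5 and under Study Procedures question 7. Both lists open in the same way: "Individuals with the following self-reported current, diagnosed medical condition(s) will be excluded automatically". Seizures close that series: "liver diseases (e.g., cirrhosis), or seizures". A consultation clause follows in both places. It starts from "Individuals with other self-reported current, diagnosed medical conditions", which go to the PI and medical monitor, and continues: "Participants with any medical condition/medication that may affect participant safety, study outcomes, or biomarker data will be excluded based on these consultations".

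Two other provisions bear on the point. The inclusion criteria under Study Procedures question 7 require participants to be healthy by self-report and a heart rate and blood pressure check. Risks question 5 allows withdrawal when the PI, medical monitor or research nurse has a safety concern.

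**The concern.** Any history of seizures and a current diagnosis of seizures define different populations. The first includes someone who had one seizure years ago and has no diagnosis today; the second, read as written, does not. Staff who screen from the exclusion lists could pass a person whom the IRB has been told is excluded, and that person belongs to a group the protocol itself names among the reported e-cigarette seizures.

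Of the seizure protections listed, the history exclusion is the only one that decides who enters. The nurse and the vital-sign monitoring act once a person is in a session. The Risks page also says that the study liquid may contain more nicotine than the participant normally uses.

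**Working it through.** **Seizure rule.** No arithmetic applies, so the check is to run each type of person through both texts.

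| Person screened | Risks question 2 | Exclusion lists (both) |
|---|---|---|
| Current, diagnosed seizure condition | Excluded | Excluded automatically |
| Recent seizure, no current diagnosis | Excluded | Only on a loose reading of the opening words |
| Remote seizure, no current diagnosis | Excluded | Not excluded automatically |
| No seizure ever | Not excluded | Not excluded |

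The texts agree on the first and last rows. The second is arguable, because the same series gives recent heart attack or stroke as an example, and those are events rather than standing diagnoses. In the third row the texts part.

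The other routes, for the third row:

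1. Healthy by self-report: a general condition that does not name seizure history.
2. Consultation clause: its second sentence is broad, but it refers back to consultations about other current, diagnosed conditions, and the outcome is a judgement.
3. Withdrawal for safety concerns: permissive, and it needs someone to learn of the history and raise it.

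Each can exclude such a person. None must.

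**Product use in the same answer.** Risks question 2 supports its respiratory statement by the "limited ECIG use that occurs in each session (10 puffs plus a 60 minute ad lib use period". The Procedure text under Study Procedures question 7 gives something else: "participants will sample the session-specific product (2 puffs) followed by a 1 hour rest period". The session clock there runs as follows:

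- 0 to 30 min: rest, 30 min
- 30 to 90: two sample puffs and rest, 60 min
- 90 to 100: CO check and subjective measures, 10 min
- 100 to 140: first task block, 40 min
- 140 to 200: rest, 60 min
- 200 to 240: second task block, 40 min

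30 + 60 + 10 + 40 + 60 + 40 = 240 minutes, the stated maximum. That leaves 240 − 240 = 0 minutes for ad lib use, and both hour-long blocks are rest.

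Puffs before counting the Progressive Ratio Task (PRT) are 2 + 0 = 2 at least and 2 + 10 = 12 at most. The ten come from the Multiple Choice Procedure (MCP) and depend on the choice drawn. In the PRT, puff k costs 4 × 2^(k−1) clicks, so n puffs cost 4 × (2^n − 1). No cap on puffs is stated. As an illustration only, assume 2 to 10 clicks per second throughout the 40-minute block (the rate is not in the documents):

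- 2 per second: 2 × 2,400 s = 4,800 clicks, which buys 10 puffs (4,092 clicks); session maximum 12 + 10 = 22.
- 10 per second: 24,000 clicks, which buys 12 puffs (16,380 clicks); session maximum 12 + 12 = 24.

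So the description on the Risks page cannot be rebuilt from the procedure, but the doubling cost does keep use limited.

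**The case against.** The best reply is that a seizure is an event. Read literally, a current seizure would exclude almost no one at screening, so the item must have been meant to reach further, and Risks question 2, in the same submission, says how far. That is a fair account of intent. It does not settle the wording: the lists leave staff to choose among a current disorder, a recent event and any past event, and only a different page points to the last. If any history is what was meant, the amendment merely writes it down.

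The second reply is that the healthy requirement, the consultation clause and the withdrawal provision would catch such a person, and that the baseline form or the phone and web screener may ask about past seizures. This stands in part. It means nobody can say from these documents that a person with a past seizure would in fact be enrolled. It does not turn judgement into the categorical exclusion described to the IRB.

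The third reply is that the high blood pressure exclusion is also stated on the Risks page and missing from the exclusion lists. That is true, and the lists could usefully state it. But blood pressure has a numerical limit at baseline screening (Risks question 5) and a check in the inclusion criteria. Seizure history has neither in the visible text.

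A reader might also infer that the protocol has no seizure exclusion, or that the wrong description of product use means a safeguard is missing. The documents support neither. Seizures are named in both lists, and the safeguard of limited use is carried out by the written session procedure; only its description is wrong.

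**Conclusion.** The point holds for the seizure rule. The Risks page describes an exclusion for any history of seizures that neither eligibility list contains, and the general provisions reach past seizures only by judgement. Confidence in the mismatch is high, because it rests on the text alone.

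Its practical size is unknown. The number of people with a past seizure and no current diagnosis cannot be derived from the documents, and the forms that might close the gap are not visible. It would be too strong to say that such people will be enrolled or that the study is unsafe. Sample size and analysis are untouched.

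The product-use sentence is a descriptive error and not part of this conclusion. Sessions run from the Study Procedures text, so correcting the sentence changes nothing that participants do.

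**What to change.** In both exclusion lists (Study Population question 5 and Study Procedures question 7), take seizures out of the series of current, diagnosed conditions and add any history of seizures as a separate automatic exclusion. Confirm that the screening form asks about past seizures in those terms, and add the question if it does not.

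The cost is one IRB wording amendment and a check of an existing form. The downside is probably a few more screen failures, such as people with a single remote seizure.

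Editorially, in the same amendment, replace the product-use description in Risks question 2 with what the sessions contain: two sample puffs, up to ten MCP puffs if the draw pays puffs, and whatever is earned in the PRT, with no ad lib period. Give no numerical total, since the PRT has no stated cap.
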